11.3.2 Definition of Secondary Endpoints

- Overall Survival (OS)

OS is defined as the duration from enrollment to the study (randomization) to the date of death from any cause. Subjects who are alive or lost to follow-up at the time of the analysis will be censored at the last known date they were alive.

- Overall survival at 12 months (OS12) will be determined as a binary variable indicating whether or not the subject was alive at 12 months following randomization.

- Length of hospital stay (LOS)

Length of stay will be calculated for each subject and for each unplanned in-patient admission as the difference between the admission date and the discharge date (plus 1).

- Time from hospice referral to death

Time from hospice referral to death is defined as the duration from hospice referral to the date of death from any cause. Subjects who are alive or lost to follow-up at the time of the analysis will be censored at the last known date they were alive. This endpoint will only be calculated for subjects referred to hospice.

- 30-day readmission

The 30-day readmissions will be calculated for each subject as the total number 30-day readmissions. This endpoint will only be calculated for subjects with at least one in-patient admission.

- Referral to Supportive Oncology services

Referral to Supportive Oncology will be binary variables determined for each subject indicating whether or not the patient received referrals to Palliative Care, Nutrition Services, and Social Work Services offered by the Levine Cancer Institute Department of Supportive Oncology.

- Adherence to clinical care

Adherence to clinical care will be calculated for each subject in terms of the rate of subject compliance with scheduled visits. For each subject, the number of no-shows will be calculated as a percent of all scheduled within Atrium Health visits, regardless of visit type.

- Patient satisfaction

Patient satisfaction will be assessed through the EORTC IL109 customized questionnaire. The EORTC IL109 customized questionnaire was compiled in the EORTC web-based library system and combined selected items from the PATSAT-C33 and OUT-PATSAT7 questionnaires. The selected scales and individual items included in the IL109 questionnaire are shown in Table 11.3.2

Table 11.3.2 Scoring the IL109 customized questionnaire (Appendix B)

Scoring the PATSAT IL109	Number of items (n)	Item range*	item numbers (I1, I2, ..., In)
Scales			
D/Technical Skills from PATSAT-C33	3	4	1 – 3
D/Information Exchange from PATSAT-C33	3	4	4 – 6
D/Affective Behaviour from PATSAT-C33	4	4	7 – 10
N Information from PATSAT-C33	3	4	11 – 13
N Affective Behaviour from PATSAT-C33	4	4	14 – 17
Coordination from PATSAT-C33	4	4	18 – 21
Single items			
Interaction with HCP from PATSAT-C33 altered**	3	4	22,23,24
Family involvement from PATSAT-C33	1	4	25
Access/parking from PATSAT-C33	1	4	26
Access/way from PATSAT-C33	1	4	27
Continuity from Out-PATSAT7	1	4	28
Convenience from Out-PATSAT7 altered**	2	4	29,30
Transition from Out-PATSAT7 altered**	3	4	31,32,33
Overall care from PATSAT-C33	1	4	34

D = Doctors; N = Nurses; HCP = health care professional

* “Item range” is the difference between the possible maximum and the minimum response to individual items. All items are scored 1 to 5, giving range = 4.

** Altered means selected a subset of items from an multi-item scale and are included as single items in the IL-109 questionnaire.

Scores derived from the IL109

Raw scores and standardized scores will be derived for each patient for each single-item measure and multi-item scale based on the following:

- **Raw score**

For each multi-item scale (captured in Table 11.3.2), the responses of the corresponding items will be averaged using the following formula:

Raw Score = RS = $\frac{\sum^n I}{n}$, where n represents the number of items in the multi-item scale.

For each single-item measure, the score of the concerning item corresponds to the raw score.

- **Linear transformation**

Raw scores will be standardized to a 0 – 100 range to obtain the score *S* using the following transformation:

$$S = \frac{(RS - 1)}{range} * 100$$

The following guidance will be observed to derive the above endpoints for subjects with missing response data:

Single-item measures will not be imputed; raw scores and standardized scores for unanswered single-item measures will be considered as missing values.

Within a multi-item scale, if at least half of the items have been answered, it will be assumed that the missing items have values equal to the average of those items which are present for that respondent. This is algebraically equivalent to using all the items completed and applying the formulas above to calculate the raw scores and standardized scores (i.e., the missing items are ignored when making the calculations). If at least half of the items from the scale have not been answered, the raw scores and standardized scores will be considered as missing values.

- **Average overall standardized score**

It is acknowledged that the following is not endorsed by the EORTC Data Center:

The average overall standardized score across the six multi-item measures and 13 single-item measures will be calculated for each subject as the sum of the nonmissing standardized scores divided by the number of measures contributing to the sum.

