2.1.2 Secondary Objectives

- Secondary objectives are to compare patients with and without ONN for
 - Overall survival
 - Overall survival rate at 12 months
 - Length of hospital stay
 - Time from hospice referral to death
 - 30 days readmission rate
 - Referral rate to Palliative Care, Hospice, Nutrition Services, and Social Work Services
 - Adherence to clinical care (the number of no-shows as a percent of all scheduled within Atrium Health, regardless of visit type)
 - Subject satisfaction as assessed by a EORTC IL109 customized questionnaire

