11.5.5 Secondary Analysis

Overall survival will be analyzed using Kaplan-Meier techniques. Tests of statistical significance between the arms will be carried out using the log-rank test. The 12-month survival rate will be estimated for each study arm based on the Kaplan-Meier estimates. A statistical test of significance will be carried out to compare the 12-month survival rates between the arms. This will be accomplished by pooling the standard errors of the 12-month OS rates and performing a Chi-Square test. Additional survival analyses and analysis of time from hospice referral to death will be conducted using Cox-proportional hazards models. Thirty-day readmissions will be analyzed using Poisson regression. Length of stay and adherence to clinical care will be analyzed using analysis of variance techniques. The frequencies and proportions of subjects referred to Supportive Oncology services will be calculated, alongside corresponding 95% confidence intervals estimated using the Clopper-Pearson method.

The following models will be estimated for each of the six multi-scale measures, thirteen single-item measures, and one average overall standardized score: Linear mixed models for repeated-measures will be used to analyze subject-level satisfaction as assessed through the derived endpoints of the EORTC IL109 customized questionnaire. Fixed factors included in the models will be treatment arm, sampling time (T1 and T2) and the treatment by time interaction. A random factor for subject will be included in the models to account for repeated observations on the same subject. For single-item measures, mixed-effects models for repeated ordinal outcomes will be estimated for the thirteen single-item measures using ordinal logistic regression. The response outcome may be treated as a 5-level raw score or a collapsed version (e.g., 2-level factor as raw scores 1-3 versus 4-5) as appropriate. Similarly, fixed factors included in the models will be treatment arm, sampling time (T1 and T2) and the treatment by time interaction, and a random factor for subject will be included in the models to account for repeated observations on the same subject.

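### Hospice referral is promised as a between-arm comparison but is neither defined nor compared, and time from hospice referral to death is modelled only in a subset formed after randomisation

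*Combined protocol and SAP*

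**What the plan says.** **Objective.** Section 2.1.2 introduces the list with "Secondary objectives are to compare patients with and without ONN for" and includes "Referral rate to Palliative Care, Hospice, Nutrition Services, and Social Work Services". The Synopsis also lists hospice among the referral rates. Time from hospice referral to death appears in Section 2.1.2 but not in the Synopsis.

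**Referral endpoint.** Section 11.3.2 defines binary variables "indicating whether or not the patient received referrals to Palliative Care, Nutrition Services, and Social Work Services", tied to services of the institute's Department of Supportive Oncology. Hospice is not among them.

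**Referral analysis.** Section 11.5.5: "The frequencies and proportions of subjects referred to Supportive Oncology services will be calculated, alongside corresponding 95% confidence intervals", by the Clopper-Pearson method. No test, difference or model follows.

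**Hospice interval.** Section 11.3.2: "Time from hospice referral to death is defined as the duration from hospice referral to the date of death from any cause", with censoring of subjects still alive, and "This endpoint will only be calculated for subjects referred to hospice". Section 11.5.5 assigns it to Cox models. The closing paragraph of that section reuses the models already described to estimate adjusted between-arm effects.

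**Data collection.** Section 5.4 has data that support the endpoints gathered from randomisation and then every 3 months. It gives end-points of collection for acute care use, readmissions, adherence, satisfaction and survival, and only survival continues past off-intervention. Neither Section 5.4 nor the study calendar (Section 6) names referral dates.

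**The concern.** Two things do not fit together.

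First, a stated comparative objective has no endpoint (hospice) and no comparative analysis (any referral type). Followed literally, the final report would not answer it.

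Second, the one hospice quantity that does get a comparative model is restricted to referred subjects. Section 1.1.8 describes navigators as speeding up referrals and gives referral specialist as one of their roles. Section 1.1.7 says patients with metastatic or advanced unresectable disease are navigated to the end of life. If navigation changes who is referred as well as when, the referred subsets of the two arms contain different kinds of subject. The hazard ratio then mixes a change in timing with a change in case mix. Adjustment for baseline factors does not restore the randomised comparison. At stake is a secondary result that could understate a benefit of navigation on hospice timing, or in some circumstances point against it.

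**Working it through.** **1. Objective against analysis**

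| Item | Objective (2.1.2) | Endpoint (11.3.2) | Between-arm comparison (11.5.5) |
|---|---|---|---|
| Palliative care, nutrition, social work referral | yes | yes, binary | none stated |
| Hospice referral | yes | not defined | none stated |
| Time from hospice referral to death | yes | referred subjects only | Cox model |

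Section 11.5.6 shows that the plan specifies a comparison of proportions where it wants one: for the exploratory proportion starting treatment on study, it gives Clopper-Pearson intervals and adds Fisher's exact tests.

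**2. How a change in case mix moves the referred-only contrast**

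There is no planned figure to reproduce: the documents give no hospice referral rate, timing, effect size or power. All hospice inputs here are assumptions. Only 150 evaluable subjects per arm comes from the plan (Sections 1.3 and 11.5.8).

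Let p be the fraction referred in either arm, with mean interval mC under control and mN under ONN. Let e be the extra fraction referred only under ONN, with mean mE. The referred-only ONN mean is (p·mN + e·mE)/(p + e). It falls below mC when e > p(mN − mC)/(mC − mE).

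With p = 0.50, mC = 45 days and mN = 54 days (20% longer):
- mE = 10: e > 0.50 × 9/35 = 0.129, about 13 points
- mE = 20: e > 0.50 × 9/25 = 0.18, or 18 points
- mE = 45: never

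The Cox model among referred subjects was simulated with exponential times, no censoring and 4,000 runs per row. A hazard ratio (HR) above 1 means a shorter interval with ONN.

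| Extra referrals (points) | Mean of extras (days) | mN (days) | HR | Trials with HR > 1 | Significant for shorter interval |
|---|---|---|---|---|---|
| 0 | n/a | 54 | 0.83 | 14% | 0.1% |
| 10 | 20 | 54 | 0.93 | 33% | 0.6% |
| 10 | 10 | 54 | 0.98 | 45% | 2% |
| 20 | 10 | 54 | 1.10 | 73% | 9% |
| 25 | 10 | 54 | 1.15 | 83% | 14% |
| 25 | 20 | 54 | 1.06 | 66% | 6% |
| 25 | 45 | 54 | 0.88 | 20% | 0.3% |
| 25 | 10 | 45 (no shift) | 1.33 | 97% | 47% |

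A milder case has mC = mN = 40 days and 15 extra points at 10 days. The referred-only mean falls from 40 to (50 × 40 + 15 × 10)/65 = 33.1 days, with HR about 1.21 and 24% of trials significant for a shorter interval (1,000 runs), although no subject's interval was shortened.

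**3. Whether a referral-rate comparison would be informative**

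Power = Φ{[|p2 − p1| − 1.96·√(2p̄(1 − p̄)/n)] / √([p1(1 − p1) + p2(1 − p2)]/n)}, with n = 150 per arm, two-sided 0.05 and an assumed 50% control rate. For 50% vs 65%: (0.15 − 0.1119)/0.0564 = 0.676, giving 75%. Likewise 50% vs 60% gives 41%, and 50% vs 70% gives 95%.

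**4. Whether an all-subject days measure would be a safe replacement**

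The candidate is days alive after hospice referral within 12 months of randomisation, scored 0 if never referred. Take exponential survival at the design's 6-month rates (60% vs 80%, Section 11.2) and identical hospice practice in both arms (assumed: 60% eventually referred, mean 40 days before death). The measure averages 13.8 days under control and 8.2 under ONN, a fall of about 40%. With assumed means of 20 to 60 days the fall is 42% to 39%; with 70% 6-month survival under ONN it is 17% to 19%. The proportion referred by 12 months moves the same way, 41% vs 23%. The proportion referred among those who died stays at 60% in both arms, as this set-up dictates.

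**The case against.** **A reader might infer that the hospice result will have the wrong sign.** The documents do not support that. They give no hospice rate or timing, and nothing in them shows that navigation generates extra late referrals; Section 1.1.8 speaks of speeding referrals up. With 10 extra points the true direction is attenuated but not reversed (HR 0.93 to 0.98), and with extras whose mean matches the control mean it is 0.88. Reversal of a real timing benefit needed 20 or more extra points at a 10-day mean, or 25 at 20 days. This objection stands: attenuation is the safer claim, and reversal is a possibility.

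**The referral information is not lost.** Restricting to referred subjects requires referral status, so the number referred in each arm will be known. That stands too. What is missing is a defined endpoint and a stated comparison, not the raw count. Hospice may have been left out because the endpoint is tied to one department's services, but the objective still includes it.

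**A reader might infer that referrals have no collection window.** Section 5.4 starts collection of all endpoint-supporting data at randomisation and repeats it every 3 months. Only the end of collection is unstated for referrals. That matters because stopping anti-cancer treatment for good triggers off-intervention (Section 8.1), a point at which hospice referral is plausible.

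**The stakes are limited.** This concerns secondary endpoints with no power or alpha attached. Agreed.

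**Conclusion.** The point holds in this form. The hospice part of the referral objective has no endpoint, and none of the referral rates has a specified between-arm comparison; this rests on the text alone. The Cox contrast among referred subjects is not a randomised comparison and can be attenuated, or under some assumed inputs reversed, by a different mix of referred subjects. How far depends on the number and timing of extra referrals, which the documents do not give: the illustrated hazard ratios run from 0.83 with no extra referrals to 1.15 with 25 extra late ones, when the usual referrals truly gain 20%.

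A reader might also conclude that days after hospice referral, scored 0 if never referred, should replace the interval. It should not: that measure falls when survival improves, so a survival benefit would read as less hospice use. The hospice referral rate shares this dependence and needs to be read beside overall survival.

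This is a worthwhile tidy-up of secondary endpoints, with no bearing on either co-primary conclusion.

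**What to change.** Reconcile the Synopsis and Sections 2.1.2, 11.3.2 and 11.5.5:

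1. Define hospice referral (yes/no) for all evaluable subjects, alongside the three referral variables already defined.
2. Compare each referral rate between arms as a difference with a confidence interval, accounting for the randomisation strata.
3. Report time from hospice referral to death descriptively, beside the referral rate, with no treatment-effect test.
4. Present the hospice referral rate next to overall survival, with the proportion referred among subjects who died shown descriptively.
5. State in Section 5.4 and the study calendar that referral dates are collected until off-study, as far as the existing survival follow-up allows.

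**Cost.** A few more analyses, amended wording, and a referral date to capture after off-intervention. That capture is more than an open date field: follow-up at that stage is best-effort contact about every 6 months (Section 6, footnote 10), and some subjects will have moved to other institutions (Section 8.1), so dates will be incomplete for them. No extra visits are needed.

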5.4 Duration of Data Acquisition

Underlying primary data needed to support study endpoints will be acquired by trained study conduct research staff. For each subject, this will be done starting at the day of randomization and then on an every 3-month basis.

The duration of data acquisition will be as follows:

- For ACU, readmissions, adherence to clinical care, and subject satisfaction, the duration of data acquisition will be until the subject meets the criteria for off-intervention (see Section 8.1)
- For survival data, the duration of data acquisition will be until the subject becomes off study (see Section 8.2).

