11.2 Sample Size

This study is designed with co-primary objectives to evaluate the acute care utilization and 6-month OS rate. Power and sample size calculations were primarily calculated based on the OS landmark objective. The overall type I error rate for this study is alpha = 0.05. Therefore, the co-primary endpoints were both powered at the 2-sided alpha = 0.025 significance level. We estimate that treatment with standard therapy results in median survival of 8 months. Assuming an exponential distribution, this corresponds to a 6-month survival rate of approximately 60%. Therefore, the primary OS objective of this study is designed to test the null hypothesis that the 6-month OS survival rate is \leq 60%. A total of 300 evaluable subjects enrolled in a one-to-one fashion will provide 80% power, assuming the true 6-month OS rate with Nurse Navigation is 80%. A total of 347 subjects may need to be enrolled to achieve 300 evaluable subjects. A 20% improvement in the 6-month OS rate is considered clinically relevant. This sample size will also provide at least 93% power to detect a 20% reduction in acute care visits (assuming there will be 6 acute care utilization visits per year in the control arm).

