11.5 Analysis Methods

11.5.1 Timing of Analysis

An interim analysis will occur after 100 subjects have been enrolled in the evaluable population. A second interim analysis will occur after 85 deaths have occurred in the evaluable population. A third interim analysis will occur after 120 deaths have occurred in the evaluable population. Analyses of the primary objectives will occur after 300 subjects have been enrolled in the evaluable population. A final analysis will occur when the OS censoring rate reduces to 20% or when all surviving subjects (who remain on study) are on study for at least 30 months (whichever occurs first).

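### The referral endpoint has no end of observation and is summarised as crude proportions, so if survival differs between arms the comparison mixes referral practice with survival

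*Combined protocol and SAP*

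**What the plan says.** - **Objective (Section 2.1.2).** The arms are to be compared on "Referral rate to Palliative Care, Hospice, Nutrition Services, and Social Work Services".
- **Endpoint (Section 11.3.2).** "Referral to Supportive Oncology will be binary variables determined for each subject indicating whether or not the patient received referrals" to the named services. No landmark or closing date is attached. In the same section the 12-month survival flag is tied to a fixed time after randomisation, as the 6-month flag is in Section 11.3.1.
- **Capture (Section 5.4).** Collection of endpoint data starts on the day of randomisation. Stopping points follow for two groups of data. The first reads "For ACU, readmissions, adherence to clinical care, and subject satisfaction, the duration of data acquisition will be until" off-intervention. The second is survival, which runs to off-study. Referral is in neither group, and the study calendar in Section 6 has no row for it.
- **Analysis (Section 11.5.5).** "The frequencies and proportions of subjects referred to Supportive Oncology services will be calculated", with exact 95% intervals. No between-arm test, person-time or treatment of death is specified.
- **Survival assumptions (Section 11.2).** "We estimate that treatment with standard therapy results in median survival of 8 months" and "this corresponds to a 6-month survival rate of approximately 60" per cent in the control arm, against a design alternative "assuming the true 6-month OS rate with Nurse Navigation is 80" per cent. Section 5 states the hypothesis that navigation improves survival.
- **Length of study (Section 11.5.1).** The final analysis comes at 20% censoring for survival or "when all surviving subjects (who remain on study) are on study for at least 30 months", whichever is first.

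**The concern.** An ever/never flag is comparable between arms only if both arms have the same opportunity to be flagged. Here opportunity ends at death or when capture stops. The evaluable population of Section 11.4 rightly keeps early deaths, so opportunity varies widely between subjects, and under the trial's own alternative it is longer on average with navigation. Each subject still counts as one whole unit in the denominator.

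A difference in crude proportions could then come from navigators referring more people, from navigators referring the same people sooner, or from more time alive in which to be referred. The planned summary cannot separate these. What is at stake is the interpretation of one secondary objective; the co-primary endpoints are unaffected.

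**Working it through.** **Inputs from Section 11.2.** Control median survival 8 months, exponential; navigation 6-month survival 80%.

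**Assumed, because the documents give nothing.** A referral hazard r that is constant over time and identical in the two arms, so that navigation has no effect on referral. Range: 0.02 to 0.20 per month.

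**Step 1. Reproduce the plan's figure.** S(6) = exp(−6 × ln 2 / 8) = 0.595, which agrees with the stated 60% or so.

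**Step 2. Death hazards and time alive.** Control: d = ln 2 / 8 = 0.0866 per month. Navigation: d = −ln(0.8) / 6 = 0.0372 per month. Mean time alive within t months is (1 − exp(−d·t)) / d. Over 30 months this is 10.7 months (control) versus 18.1 (navigation); over 6 months it is 4.7 versus 5.4.

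**Step 3. Proportion ever referred by time t, with death competing.**

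P(t) = r / (r + d) × (1 − exp(−(r + d)·t))

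Example, control, r = 0.05, t = 30: 0.05 / 0.1366 × (1 − exp(−4.10)) = 0.366 × 0.983 = 36.0%.

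**Step 4. Capture that stops at off-intervention.** The documents give no distribution for this time. Assume a constant rate w = 1/6 per month in both arms (mean 6 months, ignoring death). Then P = r / (r + d + w).

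Control v navigation, %, with the gap in points:

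| r per month | 30 months | 12 months | 6 months | To off-intervention (mean 6 months) |
|---|---|---|---|---|
| 0.02 | 18.0 v 28.7 (10.7) | 13.5 v 17.4 (3.8) | 8.9 v 10.2 (1.3) | 7.3 v 8.9 (1.6) |
| 0.05 | 36.0 v 53.2 (17.2) | 29.5 v 37.2 (7.7) | 20.5 v 23.4 (2.9) | 16.5 v 19.7 (3.2) |
| 0.10 | 53.4 v 71.7 (18.3) | 47.9 v 58.8 (11.0) | 36.1 v 40.9 (4.8) | 28.3 v 32.9 (4.6) |
| 0.20 | 69.8 v 84.3 (14.5) | 67.5 v 79.4 (11.9) | 57.3 v 64.0 (6.7) | 44.1 v 49.5 (5.4) |

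Every gap in the table arises with no effect of navigation on referral. Moving the assumed mean time to off-intervention between 4 and 12 months widens the last column's range to 0.9 to 8.3 points.

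**Step 5. Smaller survival difference.** With navigation 6-month survival of 70% (d = −ln(0.7) / 6 = 0.0594), the 30-month gap is 4.9 to 8.8 points.

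**Step 6. Other timing of referral.**
- *All in the first month* (hazard 0.5 or 1.0 per month for one month, then none): 37.8% v 38.7%, or 61.0% v 62.2%. The gap is about 1 point.
- *Triggered k months before death with probability 0.7 (assumed), cut at 30 months:* 0.7 × (1 − exp(−d·(30 + k))). For k = 1 this is 65.2% v 47.9%; for k = 3 it is 66.0% v 49.5%. The sign reverses.

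**Step 7. Effect of the remedy.** If the referral hazard per month alive is the same in both arms, the cause-specific hazard ratio for first referral is exactly 1 whatever the death hazards are. The 6-month cumulative incidence still shows the 1.3 to 6.7 points in the table.

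**The case against.** Several points on the other side stand, and they limit the claim.

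- **The endpoint is descriptive as planned.** Section 11.5.5 names no test or model for referral, and whether a patient was ever referred is a legitimate description of total effect. This lowers the importance. It does not remove the problem, because Section 2.1.2 states a comparison and readers will compare the arm-wise proportions.
- **The 30-month horizon is not a rule for referral.** A reader might infer from Section 11.5.1 that referrals are counted for 30 months or more. That section times the final analysis, and after off-intervention the plan schedules only survival follow-up. The 11 to 18 points are therefore a long-horizon case. Stopping capture at off-intervention would not equalise opportunity either, since Section 8.1 ends that period at a different time for each subject.
- **The survival contrast is the largest available.** With 150 per arm and two-sided alpha 0.025, 60% v 80% gives about 94% power. The stated 80% power corresponds to about 60% v 76.5%, for which the 30-month gap is 8.5 to 14.9 points.
- **The direction is not established.** A reader might infer that longer life must inflate the navigation arm's referral rate. That needs a roughly constant referral hazard, and the documents say nothing about timing. Needs are assessed at intake, so early referral is plausible, and Step 6 shows a gap near zero or reversed under other patterns.
- **Referrals before randomisation.** Because enrolment may follow the start of systemic therapy by up to 30 days, a reader might infer that earlier referrals count too. Section 5.4 starts data acquisition at randomisation, so the documents do not support that.

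**Conclusion.** The concern holds in a conditional form. The flag has no end of observation, referral has no stated capture period, and the crude proportions ignore death, so the comparison in Section 2.1.2 mixes referral practice with survival whenever survival differs.

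The size is not known from the documents. Under equal constant referral hazards of 0.02 to 0.20 per month and the design's survival contrast, the spurious gap in favour of navigation is about 11 to 18 points at 30 months, 4 to 12 at 12 months, 1.3 to 6.7 at 6 months, and about 2 to 5 if capture ends at off-intervention with an assumed mean of 6 months. It shrinks with a smaller survival difference, is about 1 point if referrals are made in the first month, and can change sign if they cluster before death.

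This is a moderate issue: a secondary endpoint, no planned test, and a cheap remedy.

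**What to change.** **Section 11.3.2.** Define each flag as a first referral to that service between randomisation and 6 months after it. Section 11.4 makes this the natural window, because each evaluable subject either completes 6 months on study or dies within them.

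**Sections 5.4 and 6.** State the referral capture period, add a calendar row, and record the referral date as well as the fact of referral.

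**Section 11.5.5.** Report the 6-month cumulative incidence of first referral by arm with death as a competing event. Compare arms with a cause-specific Cox model for time to first referral, censoring at the end of referral capture.

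**Cost.** A wording change and modest programming, plus some abstraction: referral dates must be taken from the record to month 6 even for subjects already off intervention. Hospice referral dates are needed anyway for the time from hospice referral to death.

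**What it does not solve.** Referrals after month 6 leave the headline proportion. A small survival-driven gap remains in the 6-month incidence, so it should be read beside the hazard ratio. If referral is triggered by approaching death, the referral hazard itself depends on survival and neither summary separates the two completely; the recorded dates would at least show that pattern.
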